- Use one of the attachment buttons in this section or under the Additional Information section to include supplemental information with your application. During the document upload process, you will be able to provide a brief description of the attachment.

Background

Include a brief review of existing literature in the area of your research. You should identify gaps in knowledge that should be addressed and explain how your research will address those gaps or contribute to existing knowledge in this area. For interventional research, search PubMed and ClinicalTrials.gov for duplicative ongoing and completed trials with same condition and intervention(s).

As the most common neonatal sensory disorder, infant hearing loss has an incidence of at least 1.7 per 1000 births. Early childhood hearing loss that is not identified and treated appropriately typically results in significant delays in language, cognitive, and social development, with profound later effects on education and employment. The economic costs of hearing loss are substantial: the overall lifetime medical, educational, and occupational costs due to deafness are estimated to be \$2.1 billion.⁴ The U.S. Preventive Services Task Force (USPSTF) reported that early detection and intervention of infant hearing loss decreases speech impairment, social/emotional challenges, and learning/behavioral disorders.⁵⁻⁷ The Joint Committee on Infant Hearing (JCIH) recommends that all infants be screened before 1 month of age, diagnosed before 3 months of age, and initiate treatment before 6 months of age (often referred to as the "1-3-6 rule"). Early infant hearing detection and intervention (EHDI) programs are coordinated on a state level and infant hearing healthcare is typically delivered in community clinics or health departments; however, non-adherence to diagnostic testing after failed newborn screening is a national problem. EHDI programs aim to have 90% of U.S. infants with failed infant hearing screens tested and diagnosed within 3 months of failed screening, but fall unacceptably short: only 40.6% meet that standard. Heightening the concern for life-long complications due to delayed diagnosis following a failed newborn screening, the outpatient diagnostic and hearing loss treatment process is complex and difficult for parents to navigate. Families of children with hearing loss are often uninformed regarding the EHDI process and lack peer support in obtaining care for their child. Similar problems in cancer care have been addressed with patient navigation (PN) programs, leading to improved adherence to recommended diagnostic testing after abnormal screening, improved patient care, and healthcare system cost savings. Patient navigators (PNs) are trained individuals who assess and mitigate personal/environmental barriers to promote healthcare adherence and improve access to care. Our recent randomized controlled trial performed in an academic setting demonstrated PN efficacy in infant hearing healthcare. This study, conducted in collaboration with the Kentucky EHDI program, demonstrated that PN decreased infant hearing testing non-adherence (7%) compared to the standard of care (38%; $p=0.005$). Our next step is to examine the effectiveness of PN when delivered in the diverse communities served by state EHDI systems. Guided by our Community Advisory Board (CAB), EHDI partners, and hearing healthcare stakeholders, we will conduct a type 1 hybrid effectiveness-implementation trial in 10 state-funded community hearing healthcare clinics, testing PN while simultaneously investigating implementation outcomes, factors influencing implementation, and cost-effectiveness.

To summarize the current recommendations, infants are to be screened for hearing loss in the hospital of birth prior to discharge using electrophysiologic tests. If one or both ears fail the testing, an audiologist then performs a complete diagnostic evaluation. A diagnosis of hearing loss should be made before 3 months of age and intervention with amplification should occur prior to 6 months of age. In the event of poor rehabilitation with amplification and continued failed testing, the patient should undergo cochlear implantation by 12 months of age. The benefit of early identification is that timely intervention can improve language and speech acquisition in hearing-impaired children. Our research group has assessed the age of diagnosis and age of appropriate intervention in children with hearing loss in Kentucky. We have identified a statistically significant delay in diagnosis and treatment for patients from the Appalachian region of Kentucky, and, as a result of this discovery, are examining the causative factors behind this delay. The lack of education and family support is a common theme in families that fail to follow-up or delay their follow-up significantly. We are proposing a study to examine the effect of a patient navigator to influence patient satisfaction, patient/family behavior and the age of diagnosis of pediatric hearing loss.

Objectives

List your research objectives. Please include a summary of intended research objectives in the box below.

(See grant application p. 128)

Hypothesis: PN will decrease non-adherence to obtaining infant hearing diagnosis within 3 months after birth compared to the standard of care.

Specific Aim 1: Using a stepped-wedge randomized trial design, we will test the effectiveness of PN to decrease non-adherence to receipt of infant hearing diagnosis within 3 months after birth. Delivery of PN in each community will be informed by feedback from the CAB and community stakeholders.

Specific Aim 2: Aim 2 will investigate factors associated with implementation and effectiveness outcomes across the 10 clinic sites. This aim is guided by the Consolidated Framework for Implementation Research (CFIR), using implementation constructs and outcomes recommended by Proctor et al. Sources of data for this aim will include process records as well as quantitative and qualitative data from PNs; clinic administrators, staff, and providers; and parent participants. Consistent with CFIR, we will assess PN knowledge and behaviors following completion of the PN curriculum, including intervention fidelity; PN characteristics; inner and outer setting clinic characteristics; and four key implementation outcomes: adoption, recruitment/retention, reach/penetration, and sustainability.

Specific Aim 3: Aim 3 involves incremental cost-effectiveness analyses in which net costs and net effectiveness of the intervention will be compared with that of standard of care for patients referred to OCSHCN clinics after a failed newborn hearing screen. Hypothesis: (a) PN after a failed newborn hearing screen will be cost effective compared to the standard of care from the perspective of third-party payers. We will compare net costs and effectiveness of PN compared to standard of care. Results will be expressed as a ratio of differences in observed costs to differences of observed outcomes. The perspective of this evaluation will be third party payers.

Study Design

Describe and explain the study design (e.g., observational, secondary analysis, single/double blind, parallel, crossover, deception, etc.).

- *Clinical Research:* Indicate whether subjects will be randomized and whether subjects will receive any placebo.
- *Community-Based Participatory Research:* If you are conducting [community-based participatory research \(CBPR\)](#), describe strategies for involvement of community members in the design and implementation of the study, and dissemination of results from the study.
- *Qualitative research:* Indicate ranges where flexibility is needed, if a fixed interview transcript is not available, describe interview topics including the most sensitive potential questions.
- *Research Repositories:* If the purpose of this submission is to establish a Research Repository (bank, registry) and the material you plan to collect is already available from a commercial supplier, clinical lab, or established IRB approved research repository, provide scientific justification for establishing an additional repository collecting duplicate material. Describe the repository design and operating procedures. For relevant information to include, see the [UK Research Biospecimen Bank Guidance](#) or the [UK Research Registry Guidance](#).

(See p.133 and following of attached grant submission)

For Specific Aim 1:

We will (1) use a stepped-wedge trial design to deliver patient navigation (PN) sequentially in 10 state-funded Kentucky Office for Children with Special Healthcare Needs (OCSHCN) clinics randomized to cross from usual care to PN in steps of 6-month intervals over the project period. Prior to initiation of PN at each clinic, the control condition will be the standard of care. The overall effectiveness of PN will be tested by comparing non-adherence rates during the PN condition to those during the standard of care condition. Simultaneously, we will (2) assess preliminary implementation outcomes (i.e., acceptability, adoption, recruitment/retention, and fidelity) as well as multilevel factors influencing implementation of PN in each clinic. The research will occur within 10 OCSHCN clinic offices across the state. This is a expansion of research conducted within this location approved under IRB protocol."

For Specific Aim 2:

Patient Navigators: Baseline data collection from PNs will occur immediately following study enrollment and before PN training, administered by a trained interviewer. At the conclusion of PN training, PNs will take an examination to ensure comprehension of critical principles necessary for successful navigation. A score >80% will be required to pass the training. PNs with less than a passing score will be allowed to repeat relevant training elements and retake the examination one time; if the examination is not passed on the second round, the PN will no longer be employed in this study and a new PN will be identified. For those who pass the examination and proceed to intervention delivery, PNs will (1) audio-record 10% of PN sessions (with parent permission) to allow assessment of fidelity, (2) complete a PN fidelity checklist following each PN session (6 total checklists), and (3) maintain process logs detailing time, travel, attendance, frequency and modes of contact with families, and other activities and expenses associated with PN delivery.

Approximately 6 months after completing PN training, PNs will complete post-test assessments and key informant interviews, administered by a trained interviewer. PNs will be compensated \$25 at baseline and post-test for completing the battery of assessments. In each clinic, PN will continue after the 6-month assessment time point until the end of the 2nd quarter of Y5. These data will be shared with the CAB quarterly and recommendations on additional PN training or PN modifications will be observed.

Clinic Administrators, Staff, and Providers: Approximately 6 months after crossing to the PN condition, administrators, staff, and providers from each clinic will participate in key informant interviews and complete quantitative measures administered by a trained interviewer.

Parent Participants: At the Aim 1 post-test assessment (16 weeks post-birth), parents will complete a PN satisfaction measure and questionnaires. Selected parents (N~40) will also complete a 1-hour semi-structured key informant interview exploring parents' experiences with the PN intervention.

For Specific Aim 3:

Both direct and indirect costs associated with PN will be included. Costs associated with the initial newborn hearing screen will be excluded from analyses since these costs are incurred for all infants regardless of outcomes.

Direct costs include the cost of: PN establishment (PN recruitment and training costs), program implementation (office space, PN time, PN travel and tools, PN materials, PN supervision, staff turnover), parent time and travel (travel to seek diagnostic or PN services, time

spent receiving diagnostic services), treatment costs (costs of a rescreen or diagnostic audiology appointment), nonmedical costs (potential cost savings due to earlier identification), and non-adherence costs for the clinics (no-show appointments). Research activity costs (e.g., data collection, human subject protection training of PNs) are not included.

Indirect costs include opportunity costs of time (e.g. loss of productivity/wages) for the parent(s).

Effectiveness: The measured outcome of effectiveness to which costs will be compared is the proportion of individuals in each group who achieve diagnosis by 3 months of age. We will derive these outcome data using clinic-level non-adherence rates reported monthly by EHDI, collected in Aim 1.

Aim 1 is involving the recruitment of 1120 parent-infant dyads over the course of 4 years referred for hearing testing to OCSHCN clinics all across the state of Kentucky. The research will occur within 10 OCSHCN clinic offices across the state. This is a expansion of research conducted within this location approved under IRB protocol. These patients are referred to those clinics from birthing hospitals at the time of birth because the child fails a newborn hearing test in the newborn nursery. This is one while the child is in the hospital but usually no more than 3-4 weeks after the child is born. Once the dyad is referred to that OCSHCN clinic, the clinic schedules them for their office visit in that clinic. The OCSHCN staff (not any of our research personnel) ask the parent about being contacted by the research personnel and may insert a small flyer on the study that would accompany the appointment reminder if parent would like further information. If they agree to being contacted then the OCSHCN staff send the name and contact number of the dyad to our research staff to contact about participation in the study. We do not cold call anyone and we do not go through any records to identify subjects. The potential participants are given to us by our partners at the OCSHCN. We then contact them by phone initially and go through the verbal consent over the phone. We do ask parents for additional contact methods, such as email or other contact, such a text messaging and make contact up to 5 times to participate if parent does not answer or requests return call initially. After one phone conversation, we may try to text the parent with general information to gauge further interest in participation. The text message would recall the research personnel he or she spoke to, a brief summary of the study and to contact research personnel if interested. The text would be sent only after initial contact to verify the parent phone number is correct. We will attach the contact form to initial OCSHCN referral form. We will not be going through any medical records at that OCSHCN clinic where there are going to be seen before, during, or after participation in the study. The participants provides any important medical information on the study questionnaire once informed consent is obtained. We do not have any physical contact with the proposed participants as they are likely many miles away and we do not have research personnel at the clinic. Doing the consent over the phone is the only practice way to enroll these subjects into the study in a timely manner. It is critical to do this asap because we have to involve them in the research activities within the first week or 2 after birth. If we do this by mail we will not be able to conduct this research. We will not be going through any medical records.

Aim 2 involves selected interview with certain parents or clinic staff, etc. These will be in person when possible and written informed consent is obtained for this Aim. Informed consent with parents, patient navigators and clinic administrators and personnel can include in-person or via phone/Zoom. If the parent, patient navigator or clinic administrator/personnel is unable to access REDCap, the consent will be emailed to the participant with allowance of time to review informed consent form, ask questions, and sign and date and return back to the study team with by a secure email or fax machine only accessible to research personnel. If the consenting process occurs by phone or Zoom, the parents, patient navigators or clinic administrators/personnel will be sent a link via REDCap to review & sign the consent while on the phone/Zoom with study personnel. A copy of the consent will either be emailed to them automatically via REDCap if consented electronically or the copy of the signed consent will be mailed or emailed to the participants.

Attachments

Subject Recruitment Methods & Advertising

Describe how the study team will identify and recruit subjects. Please consider the following items and provide additional information as needed so that the IRB can follow each step of the recruitment process.

- How will the study team identify potential participants?
- Who will first contact the potential subjects, and how?
- Will you use advertisements? If so, how will you distribute those?
- How and where will the research team meet with potential participants?
- If applicable, describe proposed outreach programs for recruiting women, minorities, or disparate populations.
- How you will minimize undue influence in recruitment?
- Attach copies of all recruiting and advertising materials (emails, verbal scripts, flyers, posts, messages, etc.).

For additional information on recruiting and advertising:

- [IRB Application Instructions - Advertisements](#)
- [PI Guide to Identification and Recruitment of Human Subjects for Research](#)

Aim 1 is involving the recruitment of 1120 parent-infant dyads over the course of 4 years referred for hearing testing to Office for Children with Special Health Care Needs (OCSHCN) clinics all across the state of Kentucky. The research will occur within 10 OCSHCN clinic offices across the state. This is a expansion of research conducted within this location approved under IRB protocol. These patients are referred to those clinics from birthing hospitals at the time of birth because the child fails a newborn hearing test in the newborn nursery. This is one while the child is in the hospital but usually no more than 3-4 weeks after the child is born. Once the dyad is referred to that clinic, the clinic schedules them for their office visit in that OCSHCN clinic. The clinic staff (not any of our research personnel) ask the parent about being contacted by the research personnel and may insert a small flyer on the study that would accompany the appointment reminder if parent would like further information. If they agree to being contacted then the OCSHCN staff send the name and contact number of the dyad to our research staff to contact about participation in the study. We do not cold call anyone and we do not go through any records to identify subjects. The potential participants are given to us by our partners at the

OCSHCN. We then contact them by phone and go through the verbal consent over the phone. We do ask parents for additional contact methods, such as email or other contact, such as text messaging and make contact up to 5 times to participate if parent does not answer or requests return call initially. After one phone conversation, we may try to text the parent with general information to gauge further interest in participation. The text message would recall the research personnel he or she spoke to, a brief summary of the study and to contact research personnel if interested. The text would be sent only after initial contact to verify the parent phone number is correct. We will attach this form to initial OCSHCN referral form. We will not be going through any medical records at that OCSHCN clinic where there are going to be seen before, during, or after participation in the study. The participants provides any important medical information on the study questionnaire once informed consent is obtained. We do not have any physical contact with the proposed participants as they are likely many miles away and we do not have research personnel at the clinic. Doing the consent over the phone is the only practice way to enroll these subjects into the study in a timely manner. It is critical to do this asap because we have to involve them in the research activities within the first week or 2 after birth. If we do this by mail we will not be able to conduct this research. We will not be going through any medical records.

Aim 2 involves selected interview with certain parents or clinic staff, etc. These will be in person when possible and written informed consent is obtained for this Aim. Informed consent with parents, patient navigators and clinic administrators and personnel can include in-person or via phone/Zoom. If the parent, patient navigator or clinic administrator/personnel is unable to access REDCap, the consent will be emailed to the participant with allowance of time to review informed consent form, ask questions, and sign and date and return back to the study team with by a secure email or fax machine only accessible to research personnel. If the consenting process occurs by phone or Zoom, the parents, patient navigators or clinic administrators/personnel will be sent a link via REDCap to review & sign the consent while on the phone/Zoom with study personnel. A copy of the consent will either be emailed to them automatically via REDCap if consented electronically or the copy of the signed consent will be mailed or emailed to the participants.

When using the REDCap e-consent function, a member of the study team will connect with the potential participant either through phone or Zoom, depending on the participant's capabilities. This will allow for a member of the study team to go over the consent with the participant and answer any questions he or she may have during the consent process. While on the phone or via Zoom with the potential participant, the authorized study team member obtaining consent will go into the study's REDCap form designated for the participant arm and add a new record. Once the study team member has added a new record, he or she will complete the Recruiter data collection instrument. The study team member will put his or her first and last name in the designated boxes as well as put the potential study participant's email in the designated field as shown below. To automatically send the Consent link to the participant, the study team member will check Yes to the "Send consent email to participant" question. Once all of the four fields have been filled out, the study team member will mark the form as complete. Once this Recruiter form is marked as complete, the email containing the link to the e-consent in REDCap will automatically send to participants. The participant will then click on the link to complete the e-consent. Pages of the stamped version of the consent will display in chronological order. At the end, the participant will have to answer two questions. The first one being whether or not they consent to the study. The second question asks if the research team can contact them about future studies. Once the participant marks he or her answers, They have to use the signature function to sign their name. The participant will also have to select the date. Please note that the name of the authorized person obtaining consent is located before the Next Page button. This name is pulled using REDCap piping logic from the Recruiter form that is filled out initially by the study team member. Once the participant fills out all of the questions, he or she will then click Next Page. The next page is the e-consent certification page that is built into REDCap. This provides the participants a way to certify that the information they entered is correct and that by electronically signing this is equivalent to them signing a paper consent form. If everything looks correct, the participant will check the small box in the yellow box and click Submit. After they click Submit, a copy of the signed consent form is automatically sent to their email. Participants can click on the link to view & download the signed, certified consent form. Additionally, the PDF of the signed copy of the consent is also saved in REDCap under the File Repository function so that the study team can access them at any time. A study team member will review the signed consent to make sure everything looks correct. (Please see the REDCap e-consent instructions PDF located in the Additional Information/Materials section of the e-IRB application)

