a) Patient-level recruitment will involve all parents of infants who fail an infant hearing screening and are referred to an Office for Children with Special Health Care Needs (OCSHCN) clinic for outpatient audiological testing during the window in which that clinic is implementing the patient navigation (PN) intervention. Under a sequential rollout in steps of 6-month intervals, 10 OCSHCN clinics throughout Kentucky will be randomly allocated to cross from the control condition (standard of care) to the PN condition over the project period. (OCSHCN operates 11 total clinics geographically dispersed across the state; one clinic receives too few infant audiology referrals to be included in this study.) Randomization will be stratified by clinic patient population size. No randomization will occur at the individual level. By the study's end, all clinics will have participated in the PN intervention for a minimum of 1 year and a maximum of 4 years. We anticipate approximately 1700 failed newborn screening referrals to the 10 clinics during their time in the PN intervention condition (i.e., 50 six-month periods across all 10 clinics). Based on our preliminary research, we anticipate enrolling 66% of all dyads, for a total of 1120 dyads. This enrollment would reflect an average enrollment of 22.4 participants per clinic per six-month period of the intervention condition. Because collected data will pertain to both the infant and the parent, both will be considered research participants; thus, the total planned sample size is 2240. Study eligibility will be assessed via telephone by a member of the research team who is CITI-trained in human subjects protection, and parents will provide verbal consent for their participation and their child's participation in the study. Approximately 40 already-enrolled parents will also participate in key informant qualitative interviews after a separate informed consent process. No additional inclusion/exclusion criteria will apply. At no time during this study will prospective dyads be selected by examining medical records. Dyads will be referred by the various OCSHCN clinics, and not contacted by study personnel until that time. Additionally, no survey results, or interview information (if applicable), will be added to patient records and will only be held by research personnel for the time period required by the IRB before they are destroyed.

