Costs: Both direct and indirect costs associated with PN will be included. Costs associated with the initial newborn hearing screen will be excluded from analyses since these costs are incurred for all infants regardless of outcomes. Direct costs include the cost of: PN establishment (PN recruitment and training costs), program implementation (office space, PN time, PN travel and tools, PN materials, PN supervision, staff turnover), parent time and travel (travel to seek diagnostic or PN services, time spent receiving diagnostic services), treatment costs (costs of a rescreen or diagnostic audiology appointment), nonmedical costs (potential cost savings due to earlier identification), and non-adherence costs for the clinics (no-show appointments). Research activity costs (e.g., data collection, human subject protection training of PNs) are not included. Indirect costs include opportunity costs of time (e.g. loss of productivity/wages) for the parent(s). Cost data will be collected and monitored annually throughout the study period, for both the intervention and standard of care conditions. Unit program costs will be documented as Aims 1 and 2 are implemented and sustained over the study period. Unit costs of PN and parent participant travel will be estimated using the distance between patient and clinic address/zip code multiplied by the standard GSA standard mileage rate and adding any lodging expenses (if applicable). Unit costs of PN time and PN supervision will be estimated using logs maintained by the PNs and supervisors, applying the hourly PN pay rate (or related rate for supervisor). Parent participant time will be estimated using the average wage rate for Kentucky (estimated using average wage data from the Bureau of Labor Statistics (BLS)). Unit treatment costs will be estimated using administrative charge data from the OCSHCN, aggregated at the clinic level. Unit cost savings associated with early identification will be estimated using data from the literature. Unit costs of non-adherence will be based on costs of PN time not used but spent (which may vary if services are centralized versus local) and staff costs associated with rescheduling as documented in staff logs. Loss of productivity will be estimated using an estimate of time away from work (calculated using driving distance) and lost wages for one parent, using BLS average wage statistics. Where cost related data are tied directly to PN reporting/logs, data will be reviewed and checked monthly to ensure consistency and check validity.

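### Aim 3 takes a raw difference in observed costs between conditions although patient navigation always follows standard of care within a clinic, so any calendar change in shared costs is attributed to navigation

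*Combined protocol and SAP*

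**What the plan says.** Under Objectives, Specific Aim 3, PN is compared with standard of care on net costs and net effectiveness from a third-party-payer perspective. The estimand is given in one sentence: "Results will be expressed as a ratio of differences in observed costs to differences of observed outcomes".

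Research Procedures, Specific Aim 3 (Costs), describes the inputs. On timing: "Cost data will be collected and monitored annually throughout the study period, for both the intervention and standard of care conditions". On the main clinical item: "Unit treatment costs will be estimated using administrative charge data from the OCSHCN, aggregated at the clinic level". Travel is valued at a federal mileage rate and parent time at a state average wage. Missed appointments are valued from unused navigator time and staff rescheduling logs. No rate is tied to a year.

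The order of conditions follows from the design. Study Design, Specific Aim 1: "Prior to initiation of PN at each clinic, the control condition will be the standard of care". Informed Consent Process, item (a): "Under a sequential rollout in steps of 6-month intervals, 10 OCSHCN clinics throughout Kentucky will be randomly allocated" to cross, and "all clinics will have participated in the PN intervention for a minimum of 1 year and a maximum of 4 years", which the same item totals as "50 six-month periods across all 10 clinics". Study Design, Specific Aim 2, continues PN in each clinic to the end of the second quarter of year 5.

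No section names a price year, an index, a fixed unit price or a calendar-period term for costs. Research Procedures (Parent-Infant Measures) does plan to compare testing before and during the COVID-19 pandemic.

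**The concern.** In a stepped-wedge rollout, condition and calendar time are confounded by design. A raw difference between conditions is therefore a PN effect plus whatever changed over time. For costs, the exposed items are those incurred in both conditions: rescreen and diagnostic charges, and the staff cost of no-shows and rescheduling. If visits per referral, no-show rates or prices shift in all clinics alike, PN is debited or credited with the shift.

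At stake is the numerator of the cost-effectiveness ratio, and so the hypothesis that PN is cost effective. Rising prices would count against PN. A shift in visit volume could go either way. Adding period terms to the Aim 1 test of non-adherence would not repair this, because the cost difference is formed separately.

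**Working it through.** **Consistency of the schedule inputs.** The plan expects about 1700 referrals in the PN condition and 66% enrolment: 0.66 × 1700 = 1122, against the stated 1120. Then 1120 / 50 = 22.4 per clinic per period, as stated. The 50 PN clinic-periods are therefore used below. The plan states no cost figure to reproduce.

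**What the raw difference estimates.** Let m(t) be the mean shared cost per referral at calendar time t without PN, common to all clinics apart from a clinic level, and let δ be the true PN effect on it. With clinic levels set aside, the raw difference is

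δ + [mean of m(t) over PN clinic-periods − mean of m(t) over control clinic-periods].

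The bracket is zero only if m(t) is flat or its changes happen to cancel.

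**Calendar gap within a clinic.** With T six-month periods, of which c are control, mean control time is c/2 and mean PN time is (c + T)/2. The gap is T/2 periods, whatever c is.
- Assume the cost record starts at project start. PN ends after 4.5 years, so T = 9 and the gap is 4.5 periods = 2.25 years.
- T = 8 or T = 10 gives 2.0 or 2.5 years.

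**Calendar gap pooled over clinics (T = 9, clinic-periods weighted equally).** The documents do not give the full schedule. Take as an example PN lengths of 8, 7, 7, 6, 5, 5, 4, 3, 3, 2 periods, which sum to 50. Control lengths are then 1, 2, 2, 3, 4, 4, 5, 6, 6, 7, which sum to 40, with squares summing to 196.
- Mean control time = (196/2)/40 = 2.45 periods.
- Mean PN time = ((10 × 81 − 196)/2)/50 = 6.14 periods.
- Gap = 3.69 periods = 1.845 years.

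Over all 151 sets of PN lengths that fit the stated minimum, maximum and total, the gap runs from 1.24 to 2.05 years.

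**Size if year-specific prices are used.** Drift = (1 + g)^gap − 1, as a share of the control cost of the shared items. The growth rate g is not in the documents and is assumed.

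| Gap (years) | g = 2% | g = 3% | g = 5% |
|---|---|---|---|
| 1.24 (pooled, lowest) | 2.5% | 3.7% | 6.2% |
| 1.845 (pooled, example) | 3.7% | 5.6% | 9.4% |
| 2.05 (pooled, highest) | 4.1% | 6.2% | 10.5% |
| 2.25 (within clinic) | 4.6% | 6.9% | 11.6% |

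With one price year, this price component is zero. The volume component stays: a shared change of x% in visits or no-shows between the two average dates still adds x% of the corresponding control cost to the increment.

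**Is period adjustment feasible, and at what price?** In the example schedule the number of clinics in PN by period is 0, 1, 3, 4, 6, 7, 9, 10, 10, so periods 2 to 7 contain both conditions. With equal variance per clinic-period, the information on the PN effect is proportional to:
- clinic terms only: Σ k(9 − k)/9 = 164/9 = 18.22, where k is PN length;
- clinic and period terms: 18.22 − 10 × Σ(p − 5/9)², where p is the share of clinics in PN in each period. The sum is 3.92 − 2.78 = 1.142, leaving 6.80.

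The standard error rises by √(18.22/6.80) = 1.64.

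**The case against.** The strongest reply is that the text describes unit costing with singular rates: one mileage rate, one average wage, charges aggregated by clinic. Applying one rate to every year is a natural reading, and annual collection may describe data gathering rather than valuation. Costs converted to one price year are still observed costs. This stands: price drift is conditional on a rule that the plan does not state.

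Several stronger readings are tempting, and the documents do not support them.
- A reader might infer that price growth is certainly charged to PN. The plan does not say that year-specific prices will be used.
- A reader might infer an inflated false-positive rate for a cost comparison. The plan proposes a ratio and no significance test on cost, so no such rate belongs to it.
- A reader might put a percentage on the error in the whole increment or the ratio. That needs shared and programme costs per referral, and neither is given.
- A reader might count parent wages and mileage among the exposed items. They are listed as costs but sit badly with the stated third-party-payer perspective, so this point does not rest on them. Unused navigator time has no control counterpart and is not exposed either.

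The application also refers to an attached grant submission, which is not in the text reviewed and may fix a price year. Finally, price growth works against PN, so it would not by itself produce a false claim of cost-effectiveness.

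The confounding itself is not answered. Fixed prices do not remove calendar shifts in visits, no-shows and rescheduling, and the plan itself expects the pandemic to affect testing.

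**Conclusion.** The point holds as a weakness in the stated method. The Aim 3 cost difference attributes to PN any calendar change common to all clinics in costs that both conditions incur. It does so for volume changes on any pricing rule, and for price growth only if prices are year-specific.

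At an assumed 2% to 5% annual growth, the price part would overstate the shared-item increment by about 2.5% to 11.6% of its control cost. The volume part cannot be sized in advance, and its sign is unknown. The figures assume a nine-period cost record from project start and, for the pooled gap, equal weight per clinic-period. Randomisation is stratified by clinic size, so the real weights will differ. This should be corrected in the plan. The text does not show that the reported ratio will be wrong by any particular amount.

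**What to change.** In Objectives (Specific Aim 3) and Research Procedures (Specific Aim 3, Costs), replace the raw difference with the following rule.
1. Express all costs in one stated price year with a named index, or apply one unit price per item to the resource counts of every year in both conditions.
2. Estimate the incremental cost of items incurred under both conditions from a clinic-by-period model with clinic and calendar-period (or calendar-year) terms.
3. Add the PN-only programme cost (recruitment, training, navigator time, supervision, unused navigator time) to form the numerator.
4. List which items count as shared under the stated payer perspective.

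Cost: a wording change and some added analysis, with no extra participants. Crossings fall at six-month steps while costs are collected annually, so costs in a crossing year must be dated well enough to split by condition. The statistical price is a wider interval for the shared-item increment, with a standard error about 1.6 times larger under the example schedule.
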